1.6 Data Monitoring

1.6.1 Safety Data Monitoring

Safety data will be monitored as indicated in the ISIS 416858-CSS Medical Monitoring Plan with monthly or more frequent reviews during the treatment and follow-up periods by the Sponsor Medical Monitor (or appropriately qualified designee) and PPD Medical Monitor (or appropriately qualified designee) throughout the study. Safety data to be reviewed will include selected chemistries, hematology, coagulation, ECG, vital signs and adverse events.

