Day 64	[61, 67]
Day 71	[68, 74]
Day 78	[75, 81)

Day85	[82, 88]
Day92	[89, 95]
Day99	[96, 102]
Day 106	[103, 109]
Day 113	[110, 116]
Day 120	[117, 123]
Day 127	[124, 130]
Day 134	[131, 137]
Day 141	[138, 144]
Day 148	[145, 151]
Day 155	[152, 158)
Day 162	[159, 165]
Day 169	[166, 172]
Day 176 ---	[173, 182]
Day 190	[183, 196)
Day 204	[197, 210]
Day 218	[211, 224]
Day 232	[225, 238]
Day 246	[239, 252]
Day260	[253, 266]

Table 3 Visit window for Electrocardiogram

Analysis visit	Visit window
Baseline	last non-missing measurement prior to the first dose
Day29	[2, 53]
Day78	[54, 126]
Day 176	[127, 217] -
Day260	[218, 273]

Table 4 Visit window for Chemistry panel, Hematology, and Coagulation Panel

Analysis visit	Visit window
Baseline	last non-missing measurement prior to the first dose
Day5	(2, 8]
Day 12	(9, 13]
Day 15	[14, 18]
Day22	[19, 25)
Day29	[26, 32]
Day36	[33, 42]
Day 50	[43, 56]
Day64	[57, 70]
Day78	(71,84]
Day92	[85, 98]
Day 106	[99, 112]
Day 120	[113, 126]
Day 134	[127, 140]
Day 148	(141, 154]
Day 162	[155, 168]
Day 176	[169, 182]
Day 190	[183, 196]
Day 204	[197,210]
Day 218	[211, 224]
Day 232	[225, 238]
Day 246	[239, 252]
Day 260	[253, 266]

Table 5 Visit window for Blood Urea Nitrogen, Post-Dialysis BUN, Urea Reduction Ratio

Analysis visit	Visit window
----------------	--------------

Baseline	last non-missing measurement prior to the first dose
Day36	[2, 49]
Day64	[50, 77]
Day92	[78, 105]
Day 120	[106,133]
Day 148	(134, 161]
Day 176	[162, 189]
Day 204	[190, 217]
Day 232	[218,245]
Day260	[246, 273]

Table 6 Visit window for Inflammatory Markers

Analysis visit	Visit window
Baseline	last non-missing measurement prior to the first dose
Day 15	[2, 21]
Day29	[22, 39]
Day50	[40, 63]
Day78	[64, 91]
Day 106	[92, 119]
Day 134	[120, 147]
Day 162	[148, 168]
Day 176	[169, 189]
Day 204	[190,217]
Day 232	[218, 245]
Day 260	[246,273]

2.J.2 *Populations*

The following populations will be used in this study, and any exclusion of patients from the populations will be documented and decided upon by appropriate medical, clinical, data management, and statistical personnel at Ionis Pharmaceuticals prior to unblinding.

Intent-to-Treat Population (ITT)

All subjects randomized who have received at least 1 dose of Study Drug (ISIS 416858 or placebo). Results will be summarized under the treatment to which patients were randomized.

Per Protocol Population (PPS):

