6. STUDY PROCEDURES

6.1 Study Schedule

The study period for an individual patient consists of a 4-week Screening Period for procedures followed by a 26-week Treatment Period, and a 12-week Post-Treatment Evaluation Period. Additional outpatient visits may be scheduled if required for further evaluation of an abnormal laboratory value or reported AE.

For patients participating in the PK substudy, there are 4 additional visits than those in the main study, occurring on Study Days 2, 177, 178, and 183. On Study Day 1 and at the end of the treatment period on Study Day 176, PK blood sampling is required at 1, 2, 3, 4, 6, and 10 hours after Study Drug administration. Two (2) of the 4 additional visits may be on non-dialysis days (Study Days 2 and 177).

For patients participating in the platelet subgroup, no additional visits are required. Any AEs, concomitant medications, and other safety and tolerability profiling data will be promptly reported and reviewed by Sponsor's Medical Monitor (or designee).

All required study procedures are outlined in [Appendices A, B, and C](#).

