8.5 Safety Monitoring Rules

Please refer also to the 'Guidance for Investigator' section of the Investigator's Brochure.

Baseline for the routine clinical assessments of chemistry and hematology, PD markers, assessment of clotting, PK assessments, vital signs and ECG for the study will be the last non-missing value prior to the first administration of Study Drug and prior to dialysis on Day 1 ([Appendix A](#)). If Day 1 values are not available, screening values will be used.

For baseline Urea Reduction Ratio determination, the BUN blood collection prior to dialysis as well as the post-dialysis sample on Day 1 will be used.

In addition to the standard monitoring of clinical safety parameters, the following guidelines are provided for the monitoring of selected parameters chosen based on preclinical and clinical observations.

Confirmation Guidance: At any time during the study (Treatment or Post-Treatment Evaluation Periods), any clinical laboratory results meeting the safety monitoring criteria presented below **must be confirmed** by performing measurements (ideally in the same laboratory that performed the initial measurement) on new specimens. All new specimen collections should take place as soon as possible (ideally within 7 days of the initial collection). For stopping rules, if the initial laboratory result is observed during the Treatment Period, the results from the retest **must be available** prior to administering the next dose of Study Drug (ISIS 416858 or placebo).

Re-dosing Guidance: Subjects with initial laboratory test values that reach a stopping rule must not be re-dosed until the re-test results are available. In general, subjects who do not meet the stopping rules based upon retest may continue dosing. However, the Investigator and the Sponsor Medical Monitor (or designee) should confer as to whether additional close monitoring of the subject is appropriate. If any of the stopping criteria described in [Sections 8.6.1, 8.6.2, or 8.6.3](#) are met, the subject will be permanently discontinued from further treatment with Study Drug (ISIS 416858 or placebo), evaluated fully as outlined below and in consultation with the Sponsor Medical Monitor or designee, and will be followed up in accordance with [Section 8.8](#) of the protocol.

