8.5.1 Safety Monitoring Rules for Liver Chemistry Tests

The following rules are adapted from the draft guidance for industry, "Drug-Induced Liver Injury: Premarketing Clinical Evaluation," issued by the U.S. Department of Health and Human Services, Food and Drug Administration, July 2009. For a definition of Baseline, please refer to guidance in Section 8.5 above.

In the event of an alanine aminotransferase (ALT) or aspartate aminotransferase (AST) measurement that is $> 3 \times$ ULN, or $3 \times$ baseline value if the baseline value was $>$ ULN at any time during the study (treatment and post-treatment evaluation periods), the initial measurement(s) should be confirmed as described above. Additionally, confirmatory measurements should also be performed if ALT or AST levels increase to $5 \times$ ULN.

Frequency of Repeat Measurements:

If the patient has confirmed post-baseline ALT or AST levels $> 3 \times \text{ULN}$, or $2 \times \text{baseline value}$, if the baseline value was $> \text{ULN}$ at any time during the study (treatment or post-treatment evaluation periods) that are continuing to rise, they should have their liver chemistry tests (ALT, AST, INR and total bilirubin) retested at least once-weekly until ALT and AST levels become $\leq 1.2 \times \text{ULN}$ or $\leq 1.2 \times \text{baseline}$ if the baseline value was $> \text{ULN}$.

Further Investigation into Liver Chemistry Elevations:

For patients with confirmed ALT or AST levels $> 3 \times \text{ULN}$ (or the greater of $2 \times \text{baseline value}$ or $3 \times \text{ULN}$ if baseline value was $> \text{ULN}$), the following evaluations should be performed:

1. Obtain a more detailed history of symptoms and prior and concurrent diseases
2. Obtain history for concomitant drug use (including nonprescription medications, herbal and dietary supplement preparations), alcohol use, recreational drug use, and special diets
3. Obtain a history for exposure to environmental chemical agents and travel
4. Serology for viral hepatitis (hepatitis A virus [HAV] IgM, hepatitis B surface antigen [HBsAg], hepatitis C virus [HCV] antibody, cytomegalovirus [CMV] IgM, and EBV antibody panel)
5. Serology for autoimmune hepatitis (e.g., antinuclear antibody [ANA])

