8.6.1 Stopping Rules for Liver Chemistry Elevations

In the event of confirmed laboratory results meeting the following criteria, **and the event is without an alternative explanation as discussed with the Sponsor Medical Monitor (or designee)**, dosing of a patient with Study Drug (ISIS 416858 or placebo) will be stopped permanently; values that are not confirmed due to failure to retest or missing lab values will be presumed confirmed:

1. ALT or AST > 8 x ULN, which is confirmed
2. ALT or AST > 5 x ULN, which is confirmed and persists for 2 weeks
3. ALT or AST > 3 x ULN (or the greater of 2 x baseline value or 3 x ULN if the baseline value was > ULN), which is confirmed and total bilirubin > 2 x ULN or INR > 1.5)

4. ALT or AST $> 3 \times$ ULN (or the greater of $2 \times$ baseline value or $3 \times$ ULN if the baseline value was $>$ ULN), which is confirmed, **and** with the new appearance (i.e., onset coincides with the changes in hepatic enzymes) of fatigue, nausea, vomiting, right upper quadrant pain or tenderness, fever, rash, and/or concomitant eosinophilia ($>$ ULN)

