Appendix B List of Laboratory Analytes

Appendix B List of Laboratory Analytes

Based on emerging data from this or future studies, additional tests not listed below may be performed on stored samples to better characterize the profile of ISIS 416858 or other similar oligonucleotides.

Additional Labs that May Be Performed in the Event of a Platelet Count < 75,000/mm³ are listed in Section 8.5.2.

Chemistry Panel	Other Tests	Hematology
Total protein	Hepatitis B surface antigen	Red blood cells
Albumin	Hepatitis C antibody	Hemoglobin
Glucose	HIV antibody	Hematocrit
Total bilirubin	FSH (women 55 years with 12 months of spontaneous amenorrhea only)	MCV, MCH, MCHC
Direct (conjugated) bilirubin	Serum Pregnancy test	Platelets
Indirect (unconjugated) bilirubin		
 • Count and Volume (MPV) (All Subjects) • Function and/or Activation (Subgroup Subjects only)
ALT		
AST		
GGT		
Urea Reduction Ratio	Inflammatory Markers ¹	
BUN	Hs-CRP	White blood cells (WBC)
	D-dimer	WBC Differential
	Beta-2-M	(% and absolute)
	Cardiac troponin I and T	Neutrophils
	NT-proBNP	Eosinophils
		Basophils
		Lymphocytes
		Monocytes
	Coagulation Panel	Pharmacokinetics and Immunogenicity
	aPTT (sec)	ISIS 416858 levels in plasma ²
	PT (sec)	Anti-ISIS 416858 antibodies
	INR	
	FXI antigen level and activity	

- 1 Other biomarkers may be measured, as needed; at the discretion of the Sponsor, samples will be collected and stored
- 2 Plasma PK samples may also be used for profiling of drug binding proteins, bioanalytical method validation purposes, stability assessments, metabolite assessments, immunogenicity testing (or possibly for purposes of immunogenicity assay development and/or validation), or to assess other actions of ISIS 416858 with plasma constituents or PD biomarkers
- 3 Coagulation panel analytes are to be blinded except at Screening

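### Appendix B blinds INR after Screening, yet a liver stopping rule and the weekly liver retest depend on the INR result

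*Combined protocol and SAP*

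**What the plan says.** Appendix B of the protocol puts INR in the coagulation panel with aPTT, PT and the two FXI measures. Footnote 3 reads: "Coagulation panel analytes are to be blinded except at Screening". The Pharmacodynamic Evaluations row of the synopsis repeats the blinding for the treatment and post-treatment visits and names INR. Section 4.3 blinds the Sponsor, the monitors and the site staff.

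The liver rules use INR as a working safety variable. Criterion 3 of Section 8.6.1 applies to an ALT/AST elevation above 3 x ULN (or a baseline-adjusted limit) "which is confirmed and total bilirubin > 2 x ULN or INR > 1.5". Unless another cause is agreed with the Medical Monitor, the result is a permanent stop. Section 8.5.1 asks that subjects whose confirmed elevations are still rising have their liver tests ("ALT, AST, INR and total bilirubin) retested at least once-weekly"). Section 8.5 adds a dosing hold: "Subjects with initial laboratory test values that reach a stopping rule must not be re-dosed until the re-test results are available".

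**The concern.** A mandatory stopping criterion depends on a laboratory value that another part of the same protocol withholds from the people who must act on it. Criterion 3 joins its two limbs with *or*, so raised INR is meant to be sufficient on its own when bilirubin has not reached 2 x ULN. If INR is hidden, the criterion reduces to its bilirubin limb.

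Patient safety is at stake in a small group. The dosing hold in Section 8.5 is tied to a value reaching a stopping rule, so an unseen INR does not trigger it. Continued weekly dosing would then rest on the judgment of clinicians who lack one of the results the protocol says they need. An INR above 1.5 would also be a real change in this population: Section 5.2 excludes INR above 1.4 at Screening, and Section 8.9.1 disallows warfarin and similar agents.

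**Working it through.** The plan gives no figure to reproduce. The check is a comparison of the rules, with two small counts.

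**1. Criterion 3 as logic.** The rule is: confirmed ALT/AST elevation AND (bilirubin > 2 x ULN OR INR > 1.5). With INR hidden, only the bilirubin limb can be observed. A subject with the enzyme elevation, INR > 1.5 and bilirubin ≤ 2 x ULN meets the rule, but blinded staff cannot tell.

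**2. Where INR decides.** Take confirmed elevations with bilirubin ≤ 2 x ULN, no criterion 4 symptom or eosinophilia, and no alternative explanation. Section 8.6.1 then gives:

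| ALT/AST | Enzyme-only stop | Role of INR > 1.5 |
|---|---|---|
| > 8 x ULN | Criterion 1, once confirmed | Not needed |
| > 5 to 8 x ULN | Criterion 2, only after 2 weeks | Only immediate mandatory trigger |
| > 3 to 5 x ULN | None at any time | Only mandatory trigger |

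For the middle row, criterion 2 reads: "ALT or AST > 5 x ULN, which is confirmed and persists for 2 weeks". Dosing is weekly (Section 6.1.3), so 2 weeks x 1 dose per week = about 2 doses could fall before it applies. For the bottom row the enzyme-only rules set no upper limit.

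**3. Whether INR is already measured.** SAP Section 2.1.1 uses one schedule for these panels ("Table 4 Visit window for Chemistry panel, Hematology, and Coagulation Panel"). Treatment-period visits are Days 5, 12, 15, 22, 29, 36, 50, 64, 78, 92, 106, 120, 134, 148, 162 and 176, which is 16. Post-treatment visits are Days 190, 204, 218, 232, 246 and 260, which is 6. In total, 16 + 6 = 22 post-baseline visits. INR is therefore scheduled alongside ALT/AST; what is missing is sight of the result.

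**4. Whether another section releases INR.**
- SAP 1.6.1 says: "Safety data to be reviewed will include selected chemistries, hematology, coagulation, ECG, vital signs and adverse events". It names no coagulation analyte, sets monthly review as the minimum frequency, and gives no route to the Investigator.
- Protocol 6.1 promises that "safety and tolerability profiling data will be promptly reported and reviewed by" the Medical Monitor, without addressing blinded analytes.
- SAP 2.1.4 assigns post-baseline coagulation data to unblinded staff including a clinician, but in the setting of the interim or primary-lock analysis, not continuing safety review.
- Protocol 9.5.1 has the Investigator sign every laboratory report, but does not say that blinded results appear on it.
- Protocol 8.5.3 orders INR after significant bleeding, but does not say the result is released.
- Code-breaking under Section 4.3 reveals the treatment, not the INR.
- The Section 8.6.1 default for missing values treats unconfirmed results as confirmed. It does not treat an unseen INR as exceeding 1.5.

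None of these states that a post-Screening INR, whether scheduled, for-cause or local, is shown to those applying the liver rules.

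**The case against.** The best reply is that a specific safety instruction should prevail over a general footnote. Section 8.5.1 calls INR a liver test and orders it for cause. The synopsis places the blinding under pharmacodynamics. Section 8.5 allows confirmation in another laboratory and requires that, for stopping rules, the retest be available before the next dose. Nothing bars an Investigator from ordering a local INR. The medical monitors are said to review coagulation data. The list of notes to file includes titles on blinded safety reviews, unblinding of one patient's laboratory data and an unblinded local laboratory entity, so a route may have existed in practice.

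The reply also limits the size. The other criteria and the bilirubin limb work. ALT/AST is visible and prompts confirmation and contact with the Medical Monitor, and an adverse event can end dosing under Section 8.7. If an initial value above 5 x ULN is taken as reaching criterion 2, the Section 8.5 hold would reduce the 2-dose figure.

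The points about size stand. The argument about access does not settle the conflict. Reading the specific rule as overriding the footnote is sensible, but the protocol does not say so, and the synopsis names INR among the blinded parameters. Permission to use another laboratory is not permission to see a blinded analyte. The notes to file are known only by title.

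**Conclusion.** The concern holds. Footnote 3 and the INR parts of Sections 8.5.1 and 8.6.1 cannot all be followed as written. This is a conflict between stated rules, not a missing detail. It should be corrected, but it does not disable liver monitoring as a whole.

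The effect is confined to the two lower rows of the table above. Its frequency is unknown, because the documents give no rate of ALT/AST elevation; the number of subjects is likely to be small. The 2-dose figure follows from the written rules alone, and clinical judgment may stop dosing sooner. The conclusion assumes that footnote 3 is applied literally and that no document outside the set (the Medical Monitoring Plan, the Safety Management Plan or the text of the notes to file) already releases INR. If one does, the defect is a missing cross-reference.

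**What to change.** Amend footnote 3 so that INR, including for-cause and local results, goes to the Investigator and the Sponsor Medical Monitor whenever ALT/AST meets a threshold in Section 8.5.1 or 8.6.1. Alternatively, have the central laboratory issue an alert when INR exceeds 1.5 in that situation. Keep aPTT, FXI activity and FXI antigen blinded. Carry the same exemption into the synopsis wording on pharmacodynamic evaluations. If a release route already exists elsewhere, cite it in the footnote.

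The cost is a text edit and a small conditional-release or alert set-up at the central laboratory. No extra scheduled draws are needed. The drawback is a slight risk of unblinding in the few subjects concerned. The 13-week monkey study in Section 2.3.3.3 found no effect on PT, which suggests INR would reveal little about treatment, although these are animal data.

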Appendix C PK Sampling Schedule

PK Sampling Schedule for All Subjects:

Period	Treatment (26 Weeks)								Post-Treatment Evaluation (12 Weeks)			
	Week	W1	W2	W5	W9	W13	W17	W22	W26	W28	W30	W34
Study Day	D1	D8	D29	D57	D85	D113	D148	D176	D190	D204	D232	D260
Blood Sampling Time	Pre-dialysis	Pre-dialysis	Pre-dialysis	Pre-dialysis	Pre-dialysis	Pre-dialysis	Pre-dialysis	Pre-dialysis	Pre-dialysis	Pre-dialysis	Pre-dialysis	Pre-dialysis

Additional PK Sampling Schedule for PK Subgroup Only:

D1	D2	D176	D177	D178	D183
Blood: First sample Pre-dose (taken pre-dialysis) and rest of samples Post SC injection at 1, 2, 3, 4, 6, and 10 hours Post SC Injection	Blood: 24-hour post the D1 dose (pre-dialysis)	Blood: First sample Pre-dose (taken pre-dialysis) and rest of samples Post SC injection at 1, 2, 3, 4, 6, and 10 hours Post SC Injection	Blood: 24-hour post D176dose (pre-dialysis)	Blood: 48-hour post D176dose (pre-dialysis)	Blood: 168-hour post D176dose (pre-dialysis)

Note: PK Subgroup subjects will also complete all the regularly scheduled visits and PK sampling schedule
The regular visit Day 8 PK sample constitutes the 168-hour sample for Day 1 of the PK Subgroup

**Appendix D Grading Scale for Adverse Events Relating to
Laboratory Abnormalities**

Appendix D Grading Scale for Adverse Events Relating to Laboratory Abnormalities

The following grading recommendations for adverse events relating to lab test abnormalities are based upon the Common Terminology Criteria for Adverse Events (CTCAE) Version 4.03, June 2010.

Adverse Event	Mild	Moderate	Severe
Hematology			
aPTT prolonged	>ULN - 1.5 x U.N	>1.5 - 2.5 x U.N	>2.5 x ULN; hemorrhage
Eosinophils increased*	650 - 1,500 cell/mm ³	1,501 - 5,000 cell/mm ³	>5,000 cell/mm ³
Fibrinogen decreased	<1.0 - 0.75 x LLN or <25% decrease from baseline	<0.75 - 0.5 x LLN or 25 - <50% decrease from baseline	<0.5 x LLN or <25% decrease from baseline
Hemoglobin decreased (Anemia)	Hemoglobin (Hgb) <LLN - 10.0 g/dL; <LLN - 6.2 mmol/L; <LLN - 100 g/L	Hgb <10.0 - 8.0 g/dL; <6.2 - 4.9 mmol/L; <100 - 80 g/L	Hgb <8.0 g/dL; <4.9 mmol/L; <80 g/L; transfusion indicated
Hemoglobin increased	Increase in >0 - 2 g/dL above baseline if baseline is above LLN	Increase in >2 - 4 g/dL above LLN or above baseline if baseline is above LLN	Increase in >4 g/dL above u.N or above baseline if baseline is above ULN
INR increased	>1 - 1.5 x ULN; >1 - 1.5 times above baseline if on anticoagulation	>1.5 - 2.5 x ULN; >1.5 - 2.5 times above baseline if on anticoagulation	>2.5 x ULN; >2.5 times above baseline if on anticoagulation
Lymphocyte count decreased	<LLN - 800/mm ³ ; <LLN - 0.8 x 10 ⁹ /L	<800 - 500/mm ³ ; <0.8 - 0.5 x 10 ⁹ /L	<500 /mm ³ ; <0.5 x 10 ⁹ /L
Lymphocyte count increased	-	>4000/mm ³ - 20,000/mm ³	>20,000/mm ³
Neutrophil count decreased	<LLN - 1500/mm ³ ; <LLN - 1.5 x 10 ⁹ /L	<1500 - 1000/mm ³ ; <1.5 - 1.0 x 10 ⁹ /L	<1000/mm ³ ; <1.0 x 10 ⁹ /L
Platelet count decreased	<LLN - 75,000/mm ³ ; <LLN - 75.0 x 10 ⁹ /L	<75,000 - 50,000/mm ³ ; <75.0 - 50.0 x 10 ⁹ /L	<50,000/mm ³ ; <50.0 x 10 ⁹ /L
White blood cell decreased	<LLN - 3000/mm ³ ; <LLN - 3.0 x 10 ⁹ /L	<3000 - 2000/mm ³ ; <3.0 - 2.0 x 10 ⁹ /L	<2000/mm ³ ; <2.0 x 10 ⁹ /L
Chemistry			
Acidosis	pH <normal, but >=7.3	-	pH <7.3
Alanine aminotransferase increased	>ULN - 3.0 x U.N	>3.0 - 5.0 x U.N	>5.0 x ULN
Alkaline phosphatase increased	>ULN - 2.5 x U.N	>2.5 - 5.0 x U.N	>5.0 x ULN
Alkalosis	pH >normal, but <=7.5	-	pH >7.5
Aspartate aminotransferase increased	>ULN - 3.0 x U.N	>3.0 - 5.0 x U.N	>5.0 x ULN
Blood bilirubin increased	>ULN - 1.5 x U.N	>1.5 - 3.0 x U.N	>3.0 x ULN
cardiac troponin I increased	Levels above the upper limit of normal and below the level of myocardial infarction as defined by the manufacturer	-	Levels consistent with myocardial infarction as defined by the manufacturer
cardiac troponin T increased	Levels above the upper limit of normal and below the level of myocardial infarction as defined by the manufacturer	-	Levels consistent with myocardial infarction as defined by the manufacturer
CrP increased*	>U.N - >6 ULN	>6-10 x ULN	>10 x ULN
GGT increased	>ULN - 2.5 x U.N	>2.5 - 5.0 x U.N	>5.0 x ULN
Hyperglycemia	Fasting glucose value >LLN - 160 mg/dL; Fasting glucose value >ULN - 8.9 mmol/L	Fasting glucose value >160 - 250 mg/dL; Fasting glucose value >8.9 - 13.9 mmol/L	>250 mg/dL; >13.9 mmol/L; hospitalization indicated
Hypoglycemia	>ULN - 10 mg/dL (0.59 mmol/L) without physiologic consequences	-	>ULN - 10 mg/dL (0.59 mmol/L) with physiologic consequences
Hypoalbuminemia	<LLN - 3 g/dL; <LLN - 30 g/L	<3 - 2 g/dL; <30 - 20 g/L	<2 g/dL; <20 g/L
Hypoglycemia	<LLN - 55 mg/dL; <LLN - 3.0 mmol/L	<55 mg/dL; <3.0 mmol/L	<40 mg/dL (<2.2 mmol/L) At >0 requires assistance of another person to actively administer carbohydrates, glucagon, or take other corrective actions
Lipase increased	>U.N - 1.5 x U.N	>1.5 - 2.0 x U.N	>2.0 x U.N
Serum amylase increased	>ULN - 1.5 x U.N	>1.5 - 2.0 x U.N	>2.0 x U.N

